
| | |
|--|--|
| | 
stage is to continue reservoir reduction (ADCC activities during pre-viral rebound state) and to enhance CTL responses (during the post-viral rebound state, when antibodies will capture and present antigen to APCs).
 
Should this approach work, viral load would be expected to rebound in all individuals a few weeks after the bNAbs levels decrease to subtherapeutic levels. This acute rebound would be followed by a new lower viral load set-point and perhaps a long-term remission.
 |
| PRIMARY OBJECTIVE | 
 • To determine the safety and tolerability of combination regimen including a DNA vaccine, MVA boost, TLR9 agonist and bNAbs • To determine the impact of this 5-stage regimen on post-treatment control of viral load during a treatment interruption |
| SECONDARY OBJECTIVES | 
 • To determine the immunogenicity of this 5-stage regimen • To determine the anti-reservoir activity of this this 5-stage regimen |

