10.9 ART resumption phase (Stage 6)

Viral load criteria. Based on this rationale, we propose that treatment be initiated for any one of the following outcomes: (1) viremia > 50,000 copies RNA/mL for four weeks, (2) viremia > 10,000 copies RNA/mL for 6 weeks, (3) viremia > 2000 copies RNA/ml for 12 weeks or (4) viremia > 400 copies/RNA for 24 weeks. Operationally, this will allow for an acute viremic state that will need to resolve within 12 weeks, with high-level viremia only being allowed for a brief period. Post-treatment control (defined as viremia <400 copies RNA/mL) should be achieved prior to Week 24 post-virus rebound.

For any initial viral load greater than 400 copies/mL, we will bring individuals back immediately (within 3 working days or as soon as they are available) for a repeat test.

CD4+ T cell criteria. ART will also be reinitiated if the CD4+ T cell count declines to below 350 cells/μL on two consecutive visits. If an individual demonstrates a CD4+ T cell count <350 cells/uL, we will bring them back immediately (within 3 working days or as soon as they are available) for a repeat test.

Clinical criteria. ART will also be re-initiated for any symptoms suggestive of a severe acute retroviral syndrome, particularly signs of altered mental status or viral meningitis (severe headache, neck stiffness), but including unexplained rash, lymphadenopathy, and fevers. ART will also be re-initiated at the request of the study participant and/or her primary health care provider.

Post-ART monitoring. Once ART is reinitiated, subjects will be evaluated at Weeks 4 and 8 on ART. If viral load is not below the level of quantification by Week 8, participants will be evaluated every four weeks until the viral load is confirmed to less than the level of quantification. A follow up visit will occur 24 weeks after resumption of ART.

Routine safety studies, CD4+/CD8+ T cell counts and viral load will be performed at Weeks 4, 8, 24 and at any visits required between Week 8 and Week 24 to evaluate decrease of viral load to below level of quantification. Plasma and PBMCs will be collected and cryopreserved at the time of ART resumption and at Weeks 4, 8 and 24 on ART.

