13.2 Withdrawal of Subjects from the Study

A subject may be withdrawn from the study at any time if the subject, the investigator, or the Sponsor feels that it is not in the subject's best interest to continue.

All subjects are free to withdraw from participation at any time, for any reason, specified or unspecified, and without prejudice.

Reasonable attempts will be made by the investigator to provide a reason for subject withdrawals. The reason for the subject's withdrawal from the study will be specified in the subject's source documents. As noted above, subjects who discontinue study treatment early should have an early discontinuation visit.

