15.4 Primary Efficacy Endpoint: Post-treatment Control

All subjects will undergo a treatment interruption designed to evaluate the primary outcome of “post-treatment control” (PTC), using the definition we recently used as part of the CHAMP Cohort collaboration¹³². In this study, PTCs were defined as individuals who remained off ART for ≥ 24 weeks and maintained viral loads ≤ 400 copies/mL for at least 2/3 of the time points. Viral loads > 400 HIV-1 RNA copies/mL were acceptable if the participant was subsequently able to suppress the viral load back to ≤ 400 HIV-1 RNA copies/mL and maintained virologic control for 24 weeks.

In our protocol, a combination of two bNAbs will be administered at the time ART is interrupted, and will likely have a persistent antiviral effect until levels wane to subtherapeutic levels, which we will assume to occur at about Week 12 of the ATI period. Also, we expect that in the post-ART and post-bNAb phase of the ATI that a period of acute viremia will occur, and that this could last for up several weeks. As described in Section 1.11, ART will be initiated if plasma HIV RNA levels remain consistently $> 50,000$ copies RNA/mL for four weeks, $> 10,000$ copies RNA/mL for six weeks, > 2000 copies RNA/mL for $>$

12 weeks, and > 400 copies RNA/mL > 24 weeks. In this scenario, post-treatment control will only be achieved once viremia falls below 400 copies RNA/mL and remains there for 24 weeks.

Success will hence be defined in two ways. First, subjects who fail to show any consistent rebound above 400 copies RNA/mL between Week 12 of the ATI (when bNAbs levels wane) and Week 36 of the ATI will be considered as having achieved post-treatment control. Second, subjects who exhibit a rebound and eventually achieve 24 weeks of virus control will be considered as having achieved post-treatment control.

Failure will be defined based on the need to resume ART due to high-level viremia, dropping CD4+ T cell counts, or clinical events (see Section 1.11).

The proportion of individuals who achieve our study-defined PTC will be the primary outcome.

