Primary efficacy outcome. All subjects will undergo a treatment interruption designed to evaluate the primary outcome of "post-treatment control" (PTC). The proportion of individuals who achieve PTC will be tabulated and a 2-sided 95% confidence interval obtained by exact calculations for the binomial distribution. For those who initiated ART during acute infection, a literature review indicates that no more than 15% PTC would be expected without intervention. For those who initiated during chronic infection, no more than 5% PTC would be expected. These maximum expected rates will serve as the null hypothesis for our P-value calculations. Evaluation of the acute group will be the primary analysis, while evaluation of the chronic group will be exploratory and provide initial preliminary information on generalizability.

Using standard and innovative measures of immunogenicity, we will determine the capacity of our vaccine strategies to stimulate broad, functional T cell responses against novel HIV epitopes, and comprehensively

characterize the impact of the vaccine on several innate and adaptive immune parameters. The size of the active and latent reservoirs before, during and after vaccination will be measured.

Power calculations. For the acute group, observing 6 or more PTC among N=15 (40%) will result in $P < 0.05$ versus the null hypothesis of 15%, and the study will have $\geq 80\%$ power if the true chance of PTC with intervention is $\geq 47\%$.

For the chronic group, observing even one PTC (20%) would provide some indication of promise, and observing 2 PTC (40%) would produce $P < 0.05$ versus the null hypothesis of 5%.

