| Weeks 34-60 | bNAbs + ATI | 
Participants who intend to be vaccinated should not enter this phase unless vaccinated.
 
If decision is made to be vaccinated during this phase before the participant is viremic, participant should resume ART as soon as HIV viral load is above the limit of quantification (no extended ATI).
 
If the participant's HIV viral load is already above the limit of quantification when decision is made to be vaccinated, participant should resume ART immediately.
 |

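### Section 15.4 does not require observed off-ART viral loads for post-treatment control, and it leaves several early exits from the treatment interruption unscored

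*Combined protocol and SAP*

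**What the plan says.** **Success.** Section 15.4 has two routes. The first credits "subjects who fail to show any consistent rebound above 400 copies RNA/mL between Week 12 of the ATI" and Week 36. The second credits participants who rebound and later reach 24 weeks of control.

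**Failure.** The section continues: "Failure will be defined based on the need to resume ART due to high-level viremia, dropping CD4+ T cell counts, or clinical events", with a pointer to Section 1.11.

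**Other definitions.** Section 15.4 opens by adopting a published cohort's definition, which needs at least 24 weeks off ART with 400 copies/mL or less at two thirds or more of time points. The synopsis endpoint is below 50 copies/mL, either 24 weeks after initial rebound or, for non-rebounders, through Week 24 of the interruption.

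**Ways out of the ATI that are not on the failure list.**
- Section 13.2: "All subjects are free to withdraw from participation at any time, for any reason, specified or unspecified, and without prejudice".
- Section 10.9: "ART will also be re-initiated at the request of the study participant and/or her primary health care provider".
- Section 10.8: a confirmed pregnancy leads to restart.
- Appendix C, vaccination before viremia: "participant should resume ART as soon as HIV viral load is above the limit of quantification (no extended ATI". If the participant is already viremic, restart is immediate.
- Appendix C, positive SARS-CoV-2 test or renewed shelter-in-place: restart is considered.
- Appendix C, before Week 34: the participant may opt out of the ATI.

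**Analysis set.** Section 15.1 makes intention-to-treat primary, adds a per-protocol analysis and expects little loss to follow-up. It gives no scoring or imputation rule. Section 13.3 rules out replacement after Day 0.

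**The concern.** The first route rewards the absence of a finding. In the weeks after the second antibody infusion, low viral load is expected from the antibodies alone. Section 15.4 itself assumes that their effect lasts to about ATI Week 12. Someone who leaves at Week 13 below 400 copies has shown nothing about control, yet has no rebound on record and no listed reason for restart. A participant put back on ART below 400 is in the same position, because ART then keeps the viral load down.

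Missing values are also foreseeable. Appendix C allows follow-up visits without product administration to take place remotely and does not count uncollected blood as a violation.

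The primary efficacy result is a count out of 15. If the scoring of such exits is settled after the data are seen in an open-label trial, the choice can move both the estimate and the test.

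**Working it through.** **1. How the written rules classify four participants.** Exits are placed at ATI Week 13, and control in the second route is taken to mean control off ART.

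| Participant | First success route | Second success route | Failure list | Cohort definition and synopsis endpoint |
|---|---|---|---|---|
| Withdrawn or lost, below 400 | Met as worded | Not met | Not listed | Not shown |
| Restart for request, pregnancy or an Appendix C reason, below 400 | Met as worded | Not met | Not listed (SARS-CoV-2 illness arguable) | Not met: off ART under 24 weeks |
| Same restart after consistent rebound above 400 | Not met | Not met | Not listed | Not met |
| ATI opt-out | No window to assess | Not met | Not listed | Not met |

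In the first two rows, the sentence that defines success disagrees with both other definitions in the document. In the last two, Section 15.4 gives no explicit score.

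**2. The plan's own figures.** The inputs are n = 15, null rate 15%, boundary 6 and alternative 47% (Section 15.6), with a likelihood ratio test (synopsis).
- At 6/15: 2[6 ln(0.40/0.15) + 9 ln(0.60/0.85)] = 5.50 on 1 df, P = 0.019. The exact upper tail is 0.0168.
- At 5/15: 2[5 ln(0.333/0.15) + 10 ln(0.667/0.85)] = 3.13, P = 0.077. So 6 is the boundary.
- Power: P(X ≥ 6; n = 15, p = 0.47) = 0.7875, within about a point of the stated 80%.

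**3. Effect of the scoring choice.** The documents give no dropout figure, so the number k of such exits among the 15 is an assumption. The other 15 − k have the true rate p.
- Scored PTC: P(X ≥ 6 − k; n = 15 − k, p).
- Scored non-PTC: P(X ≥ 6; n = 15 − k, p).

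| k | Scored PTC, p = 0.15 | Scored non-PTC, p = 0.15 | Scored non-PTC, p = 0.47 |
|---|---|---|---|
| 0 | 0.0168 | 0.0168 | 0.7875 |
| 1 | 0.0467 | 0.0115 | 0.7163 |
| 2 | 0.1180 | 0.0075 | 0.6299 |

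Dropping the exits gives a third answer. With 13 participants left, the likelihood ratio boundary falls to 5 (P = 0.039), the null probability is 0.0342 and power at 47% is 0.8137.

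**4. Random exits instead of a fixed count.** Suppose each participant has a 5% chance of such an exit, scored PTC. The null success rate becomes 0.15 + 0.85 × 0.05 = 0.1925, and the chance of reaching 6 of 15 is 0.052. At 10% the rate is 0.235 and the chance is 0.117.

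**5. Effect on the estimate.** Two participants are 2/15 = 13.3 percentage points. The exact 95% interval is 11.8% to 61.6% at 5/15 and 21.3% to 73.4% at 7/15.

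**The case against.** The best defense is that no sentence tells the analyst to count withdrawn or lost participants as controllers. The outcome is the proportion who achieve PTC, the primary analysis is intention-to-treat, and both the cited cohort definition and the synopsis endpoint need time off ART. A sensible analyst would score an unobserved participant as non-PTC. This stands as far as it goes: a reader might infer a deliberate policy of crediting dropouts, and the documents do not support that. But the sentence that defines success in this trial says otherwise, and a conflict among three definitions is itself the problem.

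Other strong inferences also fail:
- *Appendix C forces restarts in general.* Only the vaccination row directs a restart, and that table is guidance subject to investigator discretion. A positive test leads to a consultation, and shelter-in-place to a committee decision. Participants who intend vaccination are told not to enter the ATI unvaccinated, which limits the numbers.
- *Vaccination before rebound rules out PTC.* The synopsis does say "viral load would be expected to rebound in all individuals a few weeks after the bNAbs levels decrease to subtherapeutic levels", but on the condition that the approach works, and Section 15.4 provides for non-rebounders. A vaccinated participant who never becomes quantifiable stays off ART and can be a genuine success.
- *All such exits lack a category.* That fits restarts after rebound above 400. Earlier ones fall into the first success route.
- *Appendix C and Section 10.9 leave precedence open.* Appendix C states that it supersedes the main text.
- *One exit breaks the test.* One exit scored PTC gives 4.7%, still under 5%, though it would tip a trial sitting at 5 of 15.

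Request-based restart appears under the clinical criteria in Section 10.9, so it might be called a clinical event. However, Section 15.4 points to Section 1.11, which lists symptoms and not requests. Finally, this is a phase I/II study that disclaims exclusive reliance on P-values, and participants who discontinue are encouraged to keep attending. Both points soften the concern, but the estimate and its interval depend on the same count.

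**Conclusion.** The point holds as a defect in the primary endpoint definition. As worded, the first success route can be met without observed off-ART viral loads, the failure list is narrower than the protocol's own reasons for ending an ATI, and both conflict with the cited cohort definition and the synopsis.

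Under the stated assumption of one or two such exits among the 15 early-ART participants, the null chance of reaching 6 goes from 1.7% to 4.7% or 11.8% if they are scored PTC. If they are scored non-PTC, power at 47% goes from 78.8% to 71.6% or 63.0%. The exit counts are not in the documents; with no such exits, nothing changes. The finding concerns scoring only and does not judge any restart rule.

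**What to change.** In Section 15.4:
1. Require PTC to be shown by viral loads observed off ART across the 24-week window, and state how many missed measurements are tolerated.
2. In the primary intention-to-treat analysis, score every other participant as not PTC, including withdrawals, losses, ATI opt-outs and restarts for any reason.
3. Tabulate exits by trigger: viral load, CD4, clinical, request, pregnancy, each Appendix C reason, and opt-out.
4. Add one sensitivity analysis that excludes participants whose ATI did not start, or ended, for a named reason that is not virologic, CD4-related or clinical (opt-out, request, pregnancy, Appendix C). Name the triggers rather than citing Section 10.9, because request-based restart is in that section.
5. Reconcile Section 15.4 with the synopsis on threshold (400 versus 50 copies/mL) and window.

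The cost is a few sentences and one table. Restart triggers are already an endpoint (Section 15.3, item 4). The schedule of events already has viral loads weekly to study Week 58 and every two weeks after that, which is 13 + 6 = 19 measurements from ATI Week 12 to Week 36 (study Weeks 46 to 70). The downside is a lower observed PTC proportion and the power loss shown above if exits occur. No change to any clinical restart rule is proposed.

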15.5 Secondary Other Efficacy Endpoints

Secondary efficacy endpoints: The magnitude of response at the follow-up will be presented based on appropriate measures of central tendency (mean or median) and variability (standard deviation or interquartile range) in the T cell responses in each treatment arm.

Breadth of response will be characterized by the proportion of participants with at least one additional epitope response at week 14 (2 weeks after last vaccination) compared to their baseline response. The observed proportion of participants with response in breadth so defined will be presented with 95% Clopper-Pearson Confidence Intervals.

Other efficacy endpoints: Descriptive analyses and inferences outlined for the Primary endpoints will be applied to the Secondary and the Other endpoints. Some measures, such as integrated DNA and cell-associated RNA, will likely be better modeled by negative binomial regression, as they tend to have a skewed distribution. In addition, it may be desirable to account for the amount of input to the assays, which is readily done in negative binomial models by inclusion of an “exposure” variable. In these cases, and also when linear regression or t-tests of logarithmically transformed measurements are appropriate, we will report relative effects (percentage or fold). Because nonparametric methods such as the Wilcoxon signed-rank test produce only p-values with no quantitative effect estimates, we will use these only as confirmatory analyses or when no quantitative analysis appears viable.

Statistical analyses for all aims will follow standard good statistical practices, including assessment of model assumptions, checking for influential observations, and interpreting results in light of estimated effects and their confidence intervals, in addition to p-values.

Trajectories of continuous measures evaluated longitudinally will be examined using mixed effects models with random slopes and/or intercepts, as appropriate. Similarly, categorical measures such as the number of “new” positive responses, the number of responses that remain negative, will be investigated in generalized mixed effects models. For many reservoir measures, we anticipate using negative binomial regression, because it can properly account for skewed distributions, observed values of zero, and varying amounts of input to the assays, while estimating relative effects (fold or percentage), which will be the most meaningful scale for many of the measurements. Whenever possible, we will also calculate and analyze a single summary measure over the entire treatment period for each person, e.g., the area under

the curve and over baseline for immunogenicity measures over time. In the cases where the main interest focuses on the final measurement versus pre-treatment, we will also employ simpler methods such as paired Student's *t*-tests when feasible.

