4 STUDY DESIGN

4.1 Study Overview

We will perform an open-label, single-arm proof-of-concept study of a four-stage curative intervention in 20 HIV-infected adults for whom ART was initiated during early (n=15) or chronic (n=5) infection. All subjects will receive the same regimen and interrupt ART.

- Stage 1 (DNA prime): Subjects will first be vaccinated with HIV DNA vaccines expressing 7 unique conserved elements (CE) from p24^{Gag} at Weeks 0 and 4. An IL-12 DNA plasmid will be co-administered with the HIV DNA plasmids. DNA will be administered with electroporation.
- Stage 2 (DNA boost): These responses will then be boosted by a combination of DNA vaccines containing p24CE and full-length gag (p55) at Week 12. An IL-12 DNA plasmid will be co-administered with two HIV DNA plasmids. DNA will be administered by electroporation.
- Stage 3 (MVA boost): Subjects will receive an MVA boost at Week 20.
- Stage 4: A combination of two bNAbs (10-1074 and VRC07-523LS) will be administered at Week 24, with therapeutic levels expected to persist through Weeks 32 to 34. Starting at Week 25 and continuing through Week 33 (10 weeks), subjects will receive a weekly dose of lefitolimod. Note: As of Protocol Version 2.2, no further lefitolimod will be administered.
- Stage 5: An additional dose of the bNAbs will be administered at two days prior to Week 34. ART will be interrupted at Week 34.

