9.12 Cellular Immunologic Measurements

T cell immunogenicity. High-resolution multi-parameter flow cytometric intracellular cytokine staining (ICS) assays will be used to longitudinally monitor the induction, differentiation, and durability of HIV-specific T cell responses in the peripheral blood. PBMCs will be stimulated *in vitro* with peptides from each of the seven CE regions, or peptide pools of overlapping 15mers derived from Gag, Pol, Env, or Nef (using potential T cell epitope peptides, PTE; NIH AIDS Reagent Program). ICS will be performed on two baseline PBMC samples, and these will be compared to newly-generated T cell responses detectable in PBMCs after the electroporations (Week 20), at the peak of the vaccine response (Week 22 of the study, 2 weeks after the MVA boost), pre-ATI (Week 34 of the study, after a dose of bNAbs and 9 weekly lefitolimod injections), at Week 38 and 42 (approximately when bNAb levels are anticipated to become undetectable), and at Week 54.

The focus of our immunogenicity studies will be to measure: (1) the number of new CE-targeted CD4+ and CD8+ T cell responses elicited by therapeutic vaccination, as well as (2) the magnitude, (3) polyfunctionality (number of effector cytokines including IFN- γ , TNF- α , and IL-2 are by responding cells), and (4) cytotoxic phenotype (expression of Perforin, Granzyme B and degranulation as measured by CD107a upregulation) of the CE-targeted responses. Because the vaccine regimen may also stimulate non-CE Gag responses (with the vaccine dose that includes p55 Gag), as well as Pol and/or Env responses (with the MVA62B vaccine), we will assess these broader responses in parallel (with Nef as a negative control).

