10.6 MVA vaccination (Stage 3)

Week 20: Routine safety studies will be performed. Plasma HIV RNA levels and CD4+/CD8+ T cell counts will be measured.

Plasma and PBMCs will be collected and cryopreserved.

A urine pregnancy test will be performed and evaluated prior to MVA administration (in females of childbearing potential). If the urine pregnancy test is positive, the positive result will be confirmed with a serum pregnancy test. If the serum pregnancy test is positive, all study interventions will be discontinued.

The MVA boost will be given by intramuscular injection. Subjects will be observed for 30 minutes after vaccine administration to assess for immediate injection site reactions and adverse events.

Week 20+1: Subjects will be contacted by telephone to check on symptoms and overall response to the injection.

Week 22: Routine safety studies will be performed. Plasma HIV RNA levels and CD4+/CD8+ T cell counts will be measured.

Plasma and PBMCs will be collected and cryopreserved.

A PAXgene specimen will be collected.

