10.7 Combination bNAbs and lefitolimod administrations (Stage 4)

Week 24: Routine safety studies will be performed. Plasma HIV RNA levels and CD4+/CD8+ T cell counts will be measured. Samples will be stored to assess the impact of DNA/MVA prime-boost regimen on peak effector HIV-specific T cells, the primary immunologic outcome measurement.

Plasma and PBMCs will be collected and cryopreserved. Serum will be collected. A PAXgene specimen will be collected.

A urine pregnancy test will be performed and evaluated prior to bNAb infusion (in females of childbearing potential). If the urine pregnancy test is positive, the positive result will be confirmed with a serum pregnancy test. If the serum pregnancy test is positive, all study interventions will be discontinued.

The first dose of combination bNAbs will be administered. Subjects will be observed for 4 hours after bNAb administration to assess for immediate adverse events.

Week 24+1: Subjects will be contacted by telephone to check on symptoms and overall response to the combination bNAbs infusion.

Week 25-33: Lefitolimod (TLR9 agonist) will be administered subcutaneously weekly beginning one week (+/-3 days) after the bNAbs are administered and ending one week before the ATI. Following the initial dose at Week 25, the weekly lefitolimod doses may be administered on any day of the week provided the doses are at least 5 days apart. A total of 9 doses will be administered during this period.

Note: As of Protocol version 2.2 (Version Date 9/21/21) no further lefitolimod will be administered. See Appendix E. Participants who already received lefitolimod will continue with monitoring as below.

Routine safety monitoring studies will be performed at weeks 24, 26, 28, 30, and 32.

Plasma HIV RNA levels and CD4+/CD8+ T cell counts will also be measured at weeks 24, 28, 30, and 32.

Plasma and PBMCs will be collected and cryopreserved as outlined in Section 10.12.

Among women of childbearing potential, urine pregnancy test will be performed and evaluated prior to the first dose of lefitolimod (Week 24) then every two weeks (Weeks 26, 28, 30 and 32). If the urine pregnancy test is positive, the positive result will be confirmed with a serum pregnancy test. If the serum pregnancy test is positive, all study interventions will be discontinued.

Participants will be asked about the development of new ophthalmologic symptoms at every visit.

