10.12 Schedule of events

Schedule of Events: DNA/MVA Vaccine (Screen to Week 22, Stages 1-3)

Note: Visit windows are +/- 1 week for vaccines during Stage 1-3

| DNA/MVA Vaccine (Screen Week to 22, Stages 1-3) | S | B1 | B2 D0 | Wk 1 | W4 | W12 | W20 | W22 |
|---|----|----|----------|------|----|-----|-----|-----|
| p24CE/IL-12 | | | 1 | | 1 | | | |
| p24CE&p55/IL-12 | | | | | | 1 | | |
| MVA | | | | | | | 1 | |
| Lefitolimod | | | | | | | | |
| bNAbs | | | | | | | | |
| ATI | | | | | | | | |
| Home Nurse Visit (Optional) | | | | | | | | |
| Concomitant Medications | 1 | 1 | 1 | | 1 | 1 | 1 | 1 |
| PE (symptom) | 1 | 1 | 1 | | 1 | 1 | 1 | 1 |
| Clinical Assessment | 1 | 1 | 1 | | 1 | 1 | 1 | 1 |
| Hematology/Chemistry | 1 | 1 | 1 | 1 | 1 | 1 | 1 | 1 |
| T cell counts | 1 | 1 | 1 | 1 | 1 | 1 | 1 | 1 |
| Plasma HIV RNA | 1 | 1 | 1 | 1 | 1 | 1 | 1 | 1 |
| Pregnancy testing | 1 | | 1 | | 1 | 1 | 1 | |
| bNAb levels | | | | | | | | |
| Cryopreservation plasma | | 1 | 1 | 1 | | 1 | 1 | 1 |
| Cryopreservation PBMCs | | 1 | 1 | 1 | | 1 | 1 | 1 |
| LVBD | | 1 | 1 | | | | 1 | 1 |
| Leukapheresis (optional) | | 1* | | | | | | |
| LN FNA (optional) | | 1* | | | | | | 1 |
| GALT (optional) | | 1* | | | | | | 1 |
| Eye Exam | 1# | | | | | | | |
| ECG | 1 | | | | | | | |
| PAXGene | | | 1 | 1 | | | | 1 |
| PhenoSense Neutralizing Antibody Assay | 1 | | | | | | | |
| Serum storage | | 1^ | | | | | | |

*Optional baseline studies may be performed at any visit after screen through B2D0. #Eye exam may be done at any visit from S prior to B2D0. ^Serum can be stored at any visit within 4 weeks of or on B2D0

Schedule of Events: bNAb/TLR9 (Week 24-33, Stage 4)

Note: Visit windows are +/- 1 week for bNAbs. Week 25 lefitolimod window is 7 days and +/- 3 days after the bNAbs. Following the initial dose of lefitolimod, weekly doses may be administered on any day of the week provided the doses are at least 5 days apart.

| | W24 | W25 | W26 | W27 | W28 | W29 | W30 | W31 | W32 | W33 | |
|--|-----|-----|-----|-----|-----|-----|-----|-----|-----|-----|--|
| p24CE/IL-12 | | | | | | | | | | | |
| p24CE&p55/IL-12 | | | | | | | | | | | |
| MVA | | | | | | | | | | | |
| Lefitolimod | | 1 | 1 | 1 | 1 | 1 | 1 | 1 | 1 | 1 | Note: No more lefitolimod will be administered as of V2.2. |
| bNAbs | 1 | | | | | | | | | | |
| ATI | | | | | | | | | | | |
| Home Nurse Visit (Optional) | | | | | | | | | | | |
| Concomitant Medications | 1 | 1 | 1 | 1 | 1 | 1 | 1 | 1 | 1 | 1 | |

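### The breadth responder proportion is dated to Week 14, when no sample is taken; two weeks after the last vaccination is Week 22

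*Combined protocol and SAP*

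**What the plan says.** Section 15.5 defines breadth of response as the proportion of participants with "at least one additional epitope response at week 14 (2 weeks after last vaccination") relative to baseline, to be shown with a 95% Clopper-Pearson interval.

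Section 4.1 gives the vaccination sequence. After the first two DNA doses at Weeks 0 and 4, the responses are "boosted by a combination of DNA vaccines containing p24CE and full-length gag (p55) at Week 12", and then "Stage 3 (MVA boost): Subjects will receive an MVA boost at Week 20". Section 10.6 treats MVA as a vaccine: "The MVA boost will be given by intramuscular injection. Subjects will be observed for 30 minutes after vaccine administration".

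In the Section 10.12 schedule for Stages 1 to 3, the post-entry columns run "Wk 1 | W4 | W12 | W20 | W22".

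Section 9.12 lists ICS on two baseline samples and at Weeks 20, 22, 34, 38, 42 and 54. Week 20 is described as the sample after the electroporations. The next is "at the peak of the vaccine response (Week 22 of the study, 2 weeks after the MVA boost").

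Section 10.7 says of the Week 24 visit: "Samples will be stored to assess the impact of DNA/MVA prime-boost regimen on peak effector HIV-specific T cells, the primary immunologic outcome measurement".

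**The concern.** The time point in the analysis rule contradicts itself and has no data behind it. The week number points to the last DNA dose, while the words in parentheses point to the last vaccination, which is MVA eight weeks later (20 − 12 = 8). An analyst following Section 15.5 literally would find no sample to analyse.

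The analyst would then have to choose a substitute, and the two nearest ICS samples answer different questions. Week 20 shows breadth after the DNA doses alone. Week 22 shows breadth after DNA and MVA. In an open-label study of 20 people, that choice should be on paper before the ICS results are seen.

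Section 10.7 adds a related ambiguity. It attaches the peak T-cell response, described as the primary immunologic outcome, to a visit at which Section 9.12 plans no ICS.

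**Working it through.** This is calendar arithmetic checked against the schedule.

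**Inputs.** DNA doses at Weeks 0, 4 and 12 and MVA at Week 20 (Sections 1.3 and 4.1). PBMC cryopreservation in Stages 1 to 3 at B1, B2D0 and Weeks 1, 12, 20 and 22 (Section 10.12). ICS weeks as listed in Section 9.12. Vaccine visit window of ±1 week (Section 10.12).

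**Formula.** Endpoint week = week of last vaccination + 2.

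| Reading of last vaccination | Week given | + 2 | Visit? | PBMC draw? | ICS planned? |
|---|---|---|---|---|---|
| Last DNA dose | 12 | 14 | no | no | no |
| MVA boost | 20 | 22 | yes | yes | yes |

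The plan's figure of Week 14 is reproduced only in the first row, and that row has no sample.

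**Could a visit window supply one?** The Week 12 window covers Weeks 11 to 13 and the Week 20 window covers Weeks 19 to 21. Neither reaches Week 14.

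**Could the flexibility clause supply one?** Section 9.12 lets immunologic time points vary for participants who do not receive lefitolimod. Lefitolimod was scheduled from Week 25, and the clause adds no draw between Weeks 12 and 20.

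**Could a Week 14 draw be added now?** Not for everyone. Appendix E describes five participants already due for Week 34, who are well past Week 14.

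**Which reading does the rest of the document support?** Section 15.3 treats Stages 1 to 3 together as the vaccination series, and Stage 3 is MVA. Section 9.12 describes Week 22 by the same two-week interval, counted from MVA. The vaccination-timing table in Appendix C places the immunology endpoint in the Weeks 20 to 22 row and gives Weeks 12 to 20 no study phase. All three point to Week 22.

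**Section 10.7 against Section 9.12.** Section 9.12 puts the peak at Week 22 for both ICS and the post-vaccine tetramer work. At Week 24 it lists mass cytometry of innate cells, but neither ICS nor tetramer staining. The Week 24 PBMCs are stored, but no planned assay measures peak effector HIV-specific T cells in them.

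**The case against.** The strongest reply is that this is a clerical slip which the document nearly corrects itself. The parenthetical definition, Section 9.12 and Appendix C agree on Week 22, and only the numeral disagrees. That is largely right, and it is why the remedy is so clear. It does not make the rule executable: the numeral is part of the definition, the reason for it is not documented, and a reader could still defend Week 20 as the DNA-only time point.

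Three stronger inferences are tempting, and the documents do not support them.

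- *The immunogenicity objective loses its breadth analysis.* It does not. Section 15.5 also plans generalized mixed effects models of the number of new positive responses, and the ICS weeks for those data are set in Section 9.12. What is lost is the one breadth summary with a responder rule, a fixed time point and an interval.
- *Three sections give three dates for breadth.* Section 10.7 is about peak effector T cells and does not mention breadth. It conflicts with Section 9.12 over the peak, not with Section 15.5 over this endpoint. Since no ICS is planned at Week 12 or Week 24, the practical choice is Week 20 or Week 22.
- *The rule would label many participants as responders by chance.* The documents give no per-test error rate, no positivity criterion and no count of the epitope tests behind the rule. Any such rate would rest on assumed, independent error rates, and it has no bearing on the date.

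**Conclusion.** The point holds. The breadth responder proportion in Section 15.5, with its interval, cannot be computed as written: 0 of 20 planned participants have a scheduled Week 14 visit, PBMC draw or ICS run, and this is true whichever dose is taken as the last vaccination. Identifying Week 22 as the intended time point rests on counting MVA as a vaccination, as Sections 10.6 and 15.3 do.

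A reader might infer that so plain an error threatens the trial's conclusions. It does not. This is a descriptive secondary proportion with no stated hypothesis or power claim, and the primary endpoints, the sample size and the model of new responses do not depend on it. The severity is moderate. It still deserves correction, because it is a wrong time point in a prespecified analysis rule and leaving it would push the choice of sample to the analysis stage.

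**What to change.** In Section 15.5, replace week 14 and its parenthesis with: Week 22 (2 weeks after the MVA boost). Keeping the interval from MVA in the wording also covers participants whose Week 20 visit is postponed, as Appendix C allows. If breadth after DNA alone is of interest, name Week 20 as a separate, additional summary.

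In Section 10.7, reconcile the statement about peak effector T cells with Section 9.12. The simplest way is to move it to the Week 22 visit in Section 10.6 and describe the Week 24 storage by the assays that Sections 9.12 to 9.15 plan for that week.

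The cost is a text edit in each of these places, dated before the ICS results are analysed. No visit, blood draw or assay is added, because the Week 22 sample and ICS run and both baseline ICS runs are already planned.
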